The primary endpoint will be analyzed by analysis of covariance (ANCOVA). The least square (LS) mean, standard error (SE), and 95% CI for each treatment group, and the between group difference will be derived from ANCOVA with treatment as a factor, baseline UAS7 (continuous), and omalizumab experience for the treatment of CSU (exposed or naïve) as covariates. Data on subjects who experience an intercurrent event (ICE, i.e., exit the study prematurely or initiate prohibited or rescue medications) prior to the end of Week 12 will be set to missing. Missing UAS7 will be imputed using the Markov Chain Monte Carlo (MCMC) method. Detailed specifications for the missing data imputation will be provided in the Statistical Analysis Plan (SAP).

Binary data will be analyzed using the Cochran-Mantel-Haenszel (CMH) test, stratified by the randomization stratification factors (omalizumab experience for the treatment of CSU, exposed or naïve, and UAS7 score [16–27 or 28–42]). Data on subjects who experience an ICE prior to the end of Week 12 will be set to non-response status.

Change from baseline in continuous secondary outcomes measured at multiple post-baseline time points will be analyzed longitudinally using a mixed model. The model will include fixed effects for baseline value, randomization stratification factor, treatment, week, treatment by week interaction, baseline value by week interaction, and allow for random subject effects. The model variance-covariance matrix will be unstructured. However, if computation does not converge, the variance-covariance matrix will take the form of Toeplitz, AR (1), and compound symmetry, whichever converges first. The Kenward-Rogers approach for computing denominator degrees of freedom will be used to account appropriately for pooling of within-subject and between-subject variance estimates. Least square means and the 95% CI for the between-group difference will be estimated for each week.

Statistical Analysis cont.

Subject incidence of TEAE will be tabulated by MedDRA System Organ Class and Preferred Term and by severity and treatment relationship. Serious TEAE and TEAE leading to study discontinuation will be listed with pertinent information. Change from baseline in laboratory tests will be summarized with descriptive statistics. Details will be provided in the SAP.

2. Background

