NOEL No-observed effect level

PD Pharmacodynamics
PEF Peak expiratory flow

PID Patient identification number

PK Pharmacokinetic(s)

PP Per Protocol

PRO Patient reported outcome

SAE Serious adverse event(s)
SAP Statistical Analysis Plan

SC Subcutaneous
SE Standard error

Siglec Sialic acid-binding, immunoglobulin-like lectin

SOC System organ class

TEAE Treatment-emergent adverse event(s)

TEAESI Treatment-emergent adverse event(s) of special interest

TNF Tumor necrosis factor

μL Microliter

UAS7 Urticaria Assessment Score

ULN Upper limit of normal

UPDD Urticaria Patient Daily Diary
USP United States Pharmacopeia

VKC Vernal conjunctivitis

w/v Weight/Volume

WAO World Allergy Organization

WOCBP Women of childbearing potential

1. Protocol Synopsis

Title:	A Phase 2, Multicenter, Randomized, Double-Blind, Placebo-Controlled Study to Evaluate the Efficacy and Safety of Lirentelimab in Adult Subjects with H-1 Antihistamine Refractory Chronic Spontaneous Urticaria.
Sponsor:	Allakos Inc., [name].
Number of Sites:	Up to 70 clinical centers in the United States, Germany, and Poland
Number of Subjects:	Approximately 130

Nonclinical Background

Lirentelimab (AK002) is a humanized non-fucosylated immunoglobulin G1 (IgG1) monoclonal antibody directed against Siglec-8, a member of the CD33-related family of sialic acid-binding, immunoglobulin-like lectins (Siglecs). Siglec-8 has a restricted tissue distribution, expressed selectively on the surface of mature eosinophils and mast cells, but not in early precursors of these cell populations. In blood, binding of lirentelimab to Siglec-8 induces antibody-dependent cellular cytotoxicity (ADCC) against eosinophils, leading to rapid and sustained depletion of these cells from the circulation. In tissue, lirentelimab induces direct apoptosis of eosinophils and inhibition of mast cells.

Lirentelimab has been produced in 2 formulations: 1 for intravenous infusion (lirentelimab IV) and 1 for subcutaneous injection (lirentelimab SC) (see Test Product, Dose, and Administration).

Clinical Background

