- 4) Diagnosis of moderate-severe CSU refractory to H1-AH at a minimum of the licensed dose at the licensed frequency at the time of randomization as defined by the following:
 - Presence of hives and itch for ≥6 consecutive weeks prior to Screening Visit 1.
 - UAS7 score (range 0-42) ≥16 and HSS7 score (range 0-21) ≥8 during the 7 consecutive days prior to the screening Day -7 Phone Visit and during the 7 consecutive days prior to randomization (Day 1).
- 5) Subjects that are omalizumab-naïve or omalizumab-exposed. Omalizumab-exposed subjects are those that have demonstrated secondary loss of response, intolerance, or lack of access to biologics due to economic reasons.
- 6) Subjects must be on stable dose of H1-AH, between 1x and 4x of the licensed dose and at the licensed frequency, for treatment of CSU for at least 1 week prior to screening and willing to remain on a stable dose throughout the study.
- 7) Able and compliant with completing a daily symptom eDiary for the duration of the study and adherent to the study visit schedules.
- 8) Female subjects must be either postmenopausal (defined as no menses for 12 months without an alternative medical cause) with FSH level >30 mIU/mL at screening or surgically sterile (tubal ligation, hysterectomy, or bilateral oophorectomy) for at least 3 months, or if of childbearing potential, have a negative serum pregnancy test and agree to use a highly effective method of contraception as defined in this protocol or abstain from sexual activity, if compliant with preferred and usual lifestyle of the subject from screening until the end of the study or for 120 days following the last dose of study drug, whichever is longer.

In the case of a postmenopausal female subject with FSH level ≤30 mIU/mL at screening, the subject will be required to have a negative serum pregnancy test during the screening period and

- will also be required to have a negative urine dipstick pregnancy test prior to dosing and at each study visit.

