- 9) Male subjects with female partners of childbearing potential must agree to use a highly effective method of contraception as defined in this protocol or abstain from sexual activity from screening until the end of the study or for 120 days following the last dose of study drug, whichever is longer. All fertile men with female partners of childbearing potential should be instructed to contact the Investigator immediately if they suspect their partner might be pregnant (e.g., missed or late menstrual period) at any time during study participation.

Exclusion Criteria: Subjects will be excluded from the study if they meet any of the following criteria.

- 1) History of hypersensitivity to the study drugs or their excipients or to drugs of similar chemical classes (i.e., murine, chimeric or human antibodies).
- 2) Current use of biologics for any indication.
- 3) Demonstrated lack of primary response to treatment with a biologic therapy (e.g., omalizumab) for the treatment of CSU, defined as no response to treatment despite complete adherence to a prescribed regimen (e.g., a stable dose of omalizumab at ≥300 mg per month) for at least 3 months, based on interview at screening.
- 4) Use of any of the following treatments within 4 weeks prior to the baseline visit or any condition that in the opinion of the Investigator is likely to require such treatment(s) during the first 4 weeks of study treatment.
 - Immunosuppressive or immunomodulatory drugs, including but not limited to systemic calcineurin inhibitors (e.g., cyclosporin, tacrolimus), mTOR inhibitors (e.g., sirolimus, everolimus), anti-metabolites (e.g., azathioprine, methotrexate, 6-mercaptopurine, leflunomide, mycophenolate mofetil), alkylating agents (e.g., cyclophosphamide), and eosinophil-depleting drugs (e.g., benralizumab, pramipexole)
 - Routine (daily or every other day during 5 or more consecutive days) doses of systemic hydroxychloroquine
 - Plasmapheresis
- 5) Use of oral Janus kinase (JAK) inhibitors within 8 weeks of the baseline visit (requires discussion with Medical Monitor prior to subject enrolling in study).
- 6) Use of any of the following treatments within 3 weeks prior to the baseline visit:
 - H2 Antihistamines (H2-AH)
 - Routine (daily or every other day during 5 or more consecutive days) doses of systemic corticosteroids
 - Regular (daily or every other day) doxepin (oral)
 - Leukotriene Receptor Antagonists (LTRA) (e.g., montelukast, zafirlukast)

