2.2 Overview of Nonclinical Studies

Lirentelimab is a humanized non-fucosylated immunoglobulin G1 (IgG1) monoclonal antibody directed against Siglec-8, a member of the CD33-related family of sialic acid-binding, immunoglobulin-like lectins (Siglecs). Siglec-8 has a restricted tissue distribution, expressed selectively on the surface of mature eosinophils and mast cells, but not in early precursors of these cell populations. In blood, binding of lirentelimab to Siglec-8 induces ADCC against eosinophils, leading to rapid and sustained depletion of these cells from the circulation. In the tissue, lirentelimab induces direct apoptosis of eosinophils and inhibition of mast cells.

Lirentelimab has been produced in 2 formulations: 1 for intravenous infusion (lirentelimab IV) and 1 for subcutaneous injection (lirentelimab SC) (see Section 10. Study Treatment).

Siglec-8 is not expressed in species other than humans and high-order primates, and therefore, 2 novel mouse models have been developed for in vivo testing of lirentelimab. Lirentelimab has been studied in Siglec-8 humanized and transgenic mouse models and with human blood and tissue cells. The first model uses immunodeficient mice capable of generating human immune cells including mast cells and eosinophils when engrafted with human hematopoietic stem cells. The ability of anti-Siglec-8 antibodies to inhibit mast cell-mediated reactions has been evaluated in this model. The second rodent model is a transgenic mouse line that expresses human Siglec-8. The expression of Siglec-8 on the cell surface in these mice is restricted to eosinophils, mast cells, and basophils, a pattern of surface expression equivalent to that in humans. Anti-Siglec-8 antibodies can prevent IgE-mediated anaphylaxis in this transgenic mouse line, indicating that Siglec-8 is pharmacologically active in the model. The ability of lirentelimab to affect mast cells and eosinophils has been evaluated in this model.

Lirentelimab inhibits IgE-mediated mast cell degranulation and release of the newly formed mediator prostaglandin D2 in vitro without affecting mast cell viability. In peripheral blood preparations from normal human donors, lirentelimab shows selective depletion of eosinophils. Importantly, in a whole-blood cytokine-release assay using immobilized lirentelimab to enhance the potential for antibody crosslinking, lirentelimab did not lead to dose-dependent release of pro-inflammatory cytokines.

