8.3 Study Population

Approximately 130 male and female subjects with H1-AH refractory urticaria will be enrolled in the study. Subjects will be either biologic-naïve or biologic-exposed. Biologic-exposed subjects include those who have demonstrated secondary loss of response, intolerance, or lack of access to biologics due to economic reasons.

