8.5 Exclusion Criteria

Subjects will be excluded from the study if they meet any of the following criteria:

- 1) History of hypersensitivity to the study drugs or their excipients or to drugs of similar chemical classes (i.e., murine, chimeric or human antibodies).
- 2) Current use of biologics for any indication.
- 3) Demonstrated lack of primary response to treatment with a biologic therapy (e.g., omalizumab) for the treatment of CSU, defined as no response to treatment despite complete adherence to a prescribed regimen (e.g., a stable dose of omalizumab at ≥300 mg per month) for at least 3 months, based on interview at screening.
- 4) Use of any of the following treatments within 4 weeks prior to the baseline visit or any condition that in the opinion of the Investigator is likely to require such treatment(s) during the first 4 weeks of study treatment:
 - Immunosuppressive or immunomodulatory drugs, including but not limited to systemic calcineurin inhibitors (e.g., cyclosporin, tacrolimus), mTOR inhibitors (e.g., sirolimus, everolimus), anti-metabolites (e.g., azathioprine, methotrexate, 6-mercaptopurine, leflunomide, mycophenolate mofetil), alkylating agents (e.g., cyclophosphamide), and eosinophil-depleting drugs (e.g., pramipexole).
 - Routine (daily or every other day during 5 or more consecutive days) doses of systemic hydroxychloroquine

- Plasmapheresis
- 5) Use of oral Janus kinase (JAK) inhibitors within 8 weeks of the baseline visit (requires discussion with Medical Monitor prior to subject enrolling in study).
- 6) Use of any of the following treatments within 3 weeks prior to the baseline visit:
 - H2-AH
 - Routine (daily or every other day during 5 or more consecutive days) doses of systemic corticosteroids
 - Regular (daily or every other day) doxepin (oral)
 - Leukotriene Receptor Antagonists (LTRA) (e.g., montelukast, zafirlukast)
- 7) H1-AH use at greater than approved doses or greater than local CSU guideline recommended doses after Screening Visit 1.
- 8) Previous treatment with biologics or intravenous immunoglobulin:
 - Any cell-depleting agents including but not limited to rituximab; within 6 months prior to the baseline visit or until lymphocyte count returns to normal, whichever is longer.

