14.3 Adverse Events of Special Interest

Adverse Events of Special Interest (AESI) for this study include:

- Malignancies confirmed by histopathological report. (Mast cells and eosinophils are part of the normal immune response. By decreasing their function, lirentelimab could theoretically increase the risk of malignancy.)
- Parasitic infections confirmed by positive clinical laboratory test. (Eosinophils are believed to be involved in protecting the body from parasitic infections. Decreasing their function could theoretically increase the risk of parasitic and opportunistic infections.)
- Opportunistic infections (infections known to be more severe or occur more frequently in immunosuppressed populations) as confirmed by positive clinical laboratory test.
- Injection-related reactions and hypersensitivity reactions, including anaphylaxis.

Adverse Events of Special Interest will be assessed beginning after the time of first administration of study drug and ending on Day 155 (\pm 5) or 84 (\pm 5) days after last dose. Any new AESI (or new information related to a previously reported AESI) must be recorded in the AE eCRF and designated as an "AE of special interest."

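### The antibody classes listed in exclusion criterion 1 omit humanized antibodies, lirentelimab's own class, so a prior reaction to another humanized antibody is not clearly excluded

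*Protocol*

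**What the plan says.** **Exclusion 1.** The protocol synopsis excludes subjects with past hypersensitivity to the study drugs, to their excipients, "or to drugs of similar chemical classes (i.e., murine, chimeric or human antibodies"). Section 8.5 has the same wording, so neither place corrects the other.

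**The study drug.** The synopsis states: "Lirentelimab (AK002) is a humanized non-fucosylated immunoglobulin G1 (IgG1) monoclonal antibody directed against Siglec-8". Section 2.2 repeats the description.

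**Inclusion 5.** In the synopsis and Section 8.4: "Omalizumab-exposed subjects are those that have demonstrated secondary loss of response, intolerance, or lack of access to biologics due to economic reasons". Section 8.3 widens this from omalizumab to biologics: "Biologic-exposed subjects include those who have demonstrated secondary loss of response, intolerance, or lack of access to biologics due to economic reasons". Section 9.1 does the same. None of these places defines intolerance or says whether it includes an allergic reaction.

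**Recognised risk.** Section 14.3 lists as an adverse event of special interest: "Injection-related reactions and hypersensitivity reactions, including anaphylaxis".

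**The concern.** A class clause in a hypersensitivity exclusion is there to catch people who have reacted to drugs like the one under test. Here the clause names three antibody classes, and the class that the protocol gives for its own drug is not one of them. Followed to the letter, the criterion covers the neighbouring classes and misses the closest one.

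The stake is individual safety, not inference. The protocol treats hypersensitivity, including anaphylaxis, as a special-interest event and makes emergency provision for it in Section 14.6. The reaction symptoms listed in Section 14.4 include urticaria and pruritus, which are also symptoms of the disease under study, so a reaction may be harder to recognise early. An admitted subject could receive up to 6 double-blind injections, and up to 6 open-label ones if still eligible. The subcutaneous experience described in Section 2.5 comes from 36 healthy volunteers and does not address people with a prior antibody reaction.

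**Working it through.** No arithmetic applies. The check sets the relevant texts side by side.

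1. **What exclusion 1 covers.** Hypersensitivity to (a) the study drugs, (b) their excipients, or (c) similar chemical classes, spelled out as murine, chimeric or human antibodies. A past reaction to lirentelimab itself falls under (a). A past reaction to a murine, chimeric or human antibody falls under (c).

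2. **Is the list closed?** It is introduced by *i.e.*, which on its face gives the full content of the phrase before it. In the same set of criteria the authors mark open lists differently: exclusions 3, 4, 6 and 8 use *e.g.*, and exclusions 4 and 8 also say that a list is not limiting. Reading exclusion 1 as closed is therefore fair.

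3. **What is left out.** A past reaction to a humanized antibody other than lirentelimab. That is the class given for the study drug in the synopsis and Section 2.2.

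4. **Does another criterion close the gap?** Exclusion 2 concerns current use of biologics, exclusion 3 primary non-response, and exclusion 8 washout. None concerns past hypersensitivity. Exclusion 24 allows refusal for any other reason but is discretionary and does not mention hypersensitivity. Section 12.2.6 requires specific source documentation for inclusions 3, 4 and 6 and exclusion 3, but not for inclusion 5 or exclusion 1. It therefore does not oblige a site to record what an intolerance consisted of.

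5. **How the criteria combine.** Section 11.2 requires a subject to meet all applicable inclusion criteria and no exclusion criterion. Meeting inclusion 5 does not override exclusion 1.

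6. **What follows for a subject whose intolerance was a hypersensitivity reaction.**
   - If the earlier drug was in a listed class, exclusion 1 bars the subject, although inclusion 5 does not say so.
   - If the earlier drug was humanized, exclusion 1 read literally does not bar the subject, and only exclusion 24 remains.
   - The documents describe omalizumab only as a monoclonal anti-IgE antibody (synopsis and Section 2.4), so they do not settle which branch applies to it. Two sites could decide the same case differently.

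7. **Open-label extension.** Section 20.9.4 reapplies the criteria of Sections 8.4 and 8.5, so the same wording governs entry there. The tolerability exclusion in Section 20.9.5 concerns study drug only.

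**The case against.** The strongest reply is that this is one missing word that no careful investigator would exploit. The governing phrase refers to similar classes, the list runs from murine to human, and a physician screening for a humanized-antibody trial would hardly take it as permission to enrol someone who reacted to one. The protocol is also not strict with *i.e.*: Section 12.2.6 uses it before what look like mere examples of alternative medicine. Exclusion 24 gives two parties a veto, prior CSU treatments are reviewed at screening, every injection is followed by at least 1 hour of observation, and open-label entry is closed to subjects who tolerated study drug poorly.

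Much of this stands. It makes the bad outcome unlikely, but it relies on judgement to repair a rule that should not need it. Observation after dosing does not replace exclusion before it.

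Four stronger readings may tempt a reader, and the documents do not support them:

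- **That inclusion 5 and exclusion 1 contradict each other.** Section 11.2 applies them jointly, so exclusion 1 wins wherever it applies. Intolerance is nowhere equated with hypersensitivity, and a subject with another kind of intolerance raises no conflict.
- **That omalizumab-hypersensitive subjects certainly fall in the gap.** That requires omalizumab to be humanized, which the documents do not say.
- **That mITT membership is affected.** SAP Section 6.1.3 removes subjects who fail inclusion 3, 4, 5 or 6. An omalizumab-intolerant subject meets inclusion 5 however exclusion 1 is read, and exclusion 1 is not a trigger.
- **That special-interest events would be more frequent in the omalizumab-exposed stratum.** No figure supports this. Randomization is stratified by omalizumab experience, safety is summarized by treatment group without formal inference, and the planned adverse-event tables are not split by that stratum.

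**Conclusion.** The point holds in narrow form. As written, the safety exclusion omits the class that the protocol assigns to its own drug, so a prior hypersensitivity reaction to another humanized antibody is not clearly a bar to dosing. The result is possible, not certain.

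Its size cannot be quantified: the documents give neither the omalizumab-exposed share of the approximately 130 subjects nor the share entering through intolerance. Sample size, power, alpha, endpoints and analysis populations are not affected.

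The conclusion assumes that the class list is read as closed. It also assumes that the Study Reference Manual and eCRF, which Section 8.5 cites for documentation of the criteria and which are not available here, do not already settle the matter. It does not depend on the class of omalizumab. The change should be made because the possible harm is serious and the correction is nearly free, even though the likelihood is low or unknown.

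**What to change.** Reconcile the class list in exclusion 1, in both the synopsis and Section 8.5, with the protocol's own description of lirentelimab; the list as written lacks humanized antibodies. Have the sponsor state how exclusion 1 applies to subjects who enter through intolerance under inclusion 5 (synopsis and Section 8.4, with the parallel text in Sections 8.3 and 9.1). What that rule should be is the sponsor's clinical decision; the need is for one reading that all sites share.

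The cost is a few words in the next amendment, with matching text in the eligibility eCRF. The downside is that a few candidates become clearly ineligible. No analysis needs to change.

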2.1 Siglec-8 and Lirentelimab

Siglec-8, a member of the CD33-related family of sialic acid-binding, immunoglobulin-like lectins (Siglecs), is a transmembrane cell surface protein with restricted tissue distribution, expressed selectively on the surface of mature eosinophils and mast cells, but not in early precursors of these cell populations. Siglec-8 contains 3 extracellular immunoglobulin-like domains, a transmembrane region, and a cytoplasmic tail containing 2 tyrosine-based signaling motifs including an immunoreceptor tyrosine-based inhibitory motif (ITIM) with inhibitory function. Engagement of Siglec-8 in mast cells can result in inhibition of mediator release, and in eosinophils can induce apoptosis (Bochner, 2009). Lirentelimab also shows potent antibody-dependent cellular cytotoxicity (ADCC) against eosinophils in vivo and in vitro.

